10.3. Tertiary endpoints (Amended: 11 July 2019)

- Evaluation of CMI parameters in terms of frequencies of:
 - Antigen-specific CD4+/CD8+ T-cells identified as producing at least two markers among CD40L, IL-2, TNF- α and IFN- γ upon *in vitro* stimulation at Days 1, 29 **and** 85.
 - B-memory cells reactive with the challenge antigen(s) at Days 1, 8, 29, 64 **and** 85.
 - Plasmablasts reactive with the challenge antigens at Days 1, 8 **and** 64.
- Levels of HI antibody to chimeric vaccine strains **cH5/1N1 and cH8/1N1**:
The following aggregate variables will be calculated with 95% CI:
 - Seropositivity rates and GMTs at Days 1, 29 **and** 85.
 - Seroprotection rate (SPR) at each timepoint listed above.
 - Seroconversion rate (SCR) at Days 29 **and** 85.
 - MGI from Day 1 to each subsequent timepoint listed above.
- Assessment of the *in vivo* protective effect of the anti-stalk antibodies when transferring Day 1 **and** Day 85 pooled serum from all evaluable subjects of each vaccine groups to mice that will be subsequently challenged with cH6/1N5* or with H1N1 contained in the IIV4, using the following endpoints [refer to [APPENDIX D](#)]:

- Survival over 14 days post-challenge (day of death/euthanasia for weight loss > 25% baseline body weight) in groups of 35 mice**/serum pool/vaccine group/timepoint.
- Weight loss (change from baseline over 14 days post-challenge) in groups of 35 mice**/serum pool/vaccine group/timepoint.
- Lung virus titer in TCID₅₀/mg (\log_{10} fold change [Day 1 minus Day 85]), within challenge group.
- Pre- and post-transfer titer of human IgG to cH6/1N5* by ELISA or HI.
- Pre- and post-transfer titer of human IgG to H1N1 by ELISA or HI.
- Pre- and post-transfer titer of human IgG to recombinant HA protein by ELISA.

*Or an alternative challenge virus with similar attributes but more fit for purpose.

**If sufficient serum volumes are not available, and depending on the challenge virus pathogenicity, the number of mice can be reduced to as low as 10 mice per timepoint and virus challenge.

10.4. Determination of sample size

10.4.1. Descriptive objectives

The primary objectives of the study are to assess the reactogenicity and safety of each vaccine dose throughout the study and to describe the anti-H1 stalk immune response 28 days after each priming dose.

At the time of the protocol amendment 1, it was decided to increase the sample size from 450 to 470 subjects to take into account a larger rate of non-evaluable subjects than anticipated. The power computations from the initial protocol relative to safety endpoints were not modified because of the small sample size increase (about 2 subjects per group, from 45 to 47). The immunogenicity endpoints evaluation will be done primarily on the Per-Protocol set, which is not deemed to increase (about 43 subjects per group).

[Table 25](#) shows the true proportions associated with a 90% probability to observe an event in 45 subjects (e.g. SAE, pIMD).

Table 25 True proportions associated with a 90% probability to observe a certain number of adverse events within a group (45 subjects)

True proportion	Number of adverse events observed with > 90% probability
0.049	> 0
0.083	> 1
0.114	> 2
0.142	> 3

[Table 26](#) illustrates the 95% CIs for different possible numbers of AEs within each group.

Table 26 Two-sided exact 95% confidence intervals for the true adverse event rate at different possible observed adverse event rates (45 subjects)

Observed number of adverse events	Observed adverse event proportion	95% exact confidence interval	
		Lower limit	Upper limit
0	0.000	0.000	0.079
1	0.022	0.001	0.118
2	0.044	0.005	0.152
3	0.067	0.014	0.183
4	0.089	0.025	0.212
5	0.111	0.037	0.241
10	0.222	0.112	0.371
20	0.444	0.296	0.600
30	0.667	0.511	0.800

Table 27 presents the 95% CIs for different possible rates of immunological response within each group. A rate of unevaluable subjects of 2/45 (4%) has initially been considered for the immune response post-primary vaccination. As from protocol amendment 1, a rate of non-evaluable subjects of 4/47 (9%) has been considered for the immune response post-primary vaccination.

Table 27 Two-sided exact 95% confidence intervals for the true immunological response rate at different possible observed response rates (43 evaluable subjects)

Observed number of responses	Observed response proportion	95% exact confidence interval	
		Lower limit	Upper limit
25	0.581	0.421	0.730
30	0.698	0.539	0.828
35	0.814	0.667	0.916
40	0.930	0.809	0.985

*Response rate can be either seropositivity rate, percentages of subjects with a 4-fold increase or percentages of subjects with a 10-fold increase

The advantage of adding an adjuvant and the preference for a specific priming sequence/number of priming doses will be assessed by making use of the factorial nature of the trial design, which is summarized in **Table 28**. The anti-H1 stalk antibody titers by ELISA will primarily be modelled. The standard deviation (SD) used for the calculation cannot be obtained at the present stage due to unavailability of the final assay under development at Néomed. As a consequence, the assumed SD of \log_{10} titers was derived from study FLU-CC-SUIV-001 (e-track number 201598). In that study, anti-H1 HA stalk ELISA antibody titers were obtained using the existing anti-stalk ELISA [Pica, 2012], and the observed SD of \log_{10} titers was 0.43 (Day 42). SDs of 0.45 and 0.50 were thus considered in the present power calculations.

Table 28 Factorial study design: repartition of the subjects according to the nature of the priming sequence and to the type of adjuvant system

N evaluable subjects	1 priming dose (cH8/1N1)	1 priming dose (cH5/1N1)	2 priming doses (cH8/1N1 and cH5/1N1)	Total
AS01	43 subjects	43 subjects	43 subjects	129 subjects
AS03	43 subjects	43 subjects	43 subjects	129 subjects
No adjuvant	43 subjects	43 subjects	43 subjects	129 subjects
Total	129 subjects	129 subjects	129 subjects	387 subjects

Using a 1-way Analysis of Variance (ANOVA) power analysis in PASS 12.0.10, considering 3 pooled groups of size $n = 129$ subjects, 2-sided alpha = 0.10, SD of \log_{10} (titers) = 0.45 to 0.50, and a scenario with a maximum difference in GMTs of 2-fold (repartition type 1-1-2 or 1-2-2), we obtain the SD of group means associated with 80% power to detect differences among the means versus the alternative of equal means. This value is then converted in fold increase according to the scenario. The values are presented in [Table 29](#).

Table 29 Detectable fold increase in GMTs with 80% power (N/group = 129, 2-sided alpha = 0.10, 1-way ANOVA power analysis)

SD of \log_{10} (titers)	SD of group Means	Detectable Fold increase
0.45	0.064	1.36
0.50	0.071	1.41

10.4.2. Confirmatory objective

The most important secondary objective in the study is to establish whether an adjuvant system is needed. This evaluation will primarily be based on levels of anti-H1 stalk titers by ELISA at Day 29 and Day 85 (i.e. 28 days post-last vaccination). Power calculations were conducted for the detection of differences in GMTs between each of the 3 pooled groups of 129 subjects (AS01, AS03, no adjuvant) considering a margin of superiority of 1.5 fold. The 2-sided significance level (alpha) of each test is 0.0554; it corresponds to a critical value from a 2-sided Dunnett test (accounting for the comparison of AS01 to non adjuvanted and AS03 to non-adjuvanted) of 1.922 (2-sided alpha = 0.10, DF = 384 (129 subjects/pooled group), 3 pooled groups).

[Table 30](#) provides the power associated with different true GMT ratio values using PASS 12.0.2 Two-Sample T-Test (Superiority by a Margin) Power Analysis. Again, SDs of \log_{10} (titers) of 0.45 and 0.50 were considered. With a standard deviation of 0.45, the power reaches 80% if the actual difference is 2.14 fold or greater. Similarly, with a SD of 0.50, the power reaches 80% if the actual difference is 2.23 fold or greater.

**Table 30 Power to show a difference in means using a 1.5 superiority margin
(N/pooled group = 129, 2-sided alpha = 0.055375)**

Actual difference in means (fold-difference)	SD of log10 (titers)	Power
2.00	0.45	0.620
2.00	0.50	0.533
2.14	0.45	0.800
2.14	0.50	0.714
2.23	0.45	0.875
2.23	0.50	0.800
2.50	0.45	0.979
2.50	0.50	0.949
3.00	0.45	0.999
3.00	0.50	0.998

The success criterion for this objective can be defined as follows: *the use of the adjuvant (AS01 or AS03) will be considered justified if the lower limit of the 94.46% CI of the GMT ratio (adjuvanted vs non-adjuvanted) is > 1.50.*

10.5. Analysis sets

10.5.1. Exposed set

The Exposed Set (ES) will include all subjects with at least one vaccine administration documented:

- A safety analysis based on the ES will include all vaccinated subjects.
- An immunogenicity analysis based on the ES will include all vaccinated subjects for whom immunogenicity results are available.

The ES analyses will be performed per treatment actually administered.

10.5.2. Per-Protocol set for analysis of immunogenicity

The Per-Protocol set will be adapted by timepoint to include all eligible subjects' data up to the time of important protocol deviation, namely:

- Dose of study vaccine not according to protocol procedures and to their random assignment.
- Randomisation code broken.
- Non-compliance with the procedures and intervals defined in the protocol (refer to Table 7).
- Intake of concomitant medication/product/vaccination leading to elimination from the Per-Protocol analysis.
- Occurrence of medical condition leading to elimination from the Per-Protocol analysis (refer to Section 6.7.2).

10.6. Derived and transformed data

- The cut-off value is defined by the laboratory before the analysis and is described in Section 5.7.3. A seronegative subject is a subject whose titre is below the cut-off value. A seropositive subject is a subject whose titre is greater than or equal to the cut-off value.
- The GMTs calculations are performed by taking the anti-log of the mean of the log titre transformations. Antibody titres below the cut-off of the assay will be given an arbitrary value of half the cut-off for the purpose of GMT calculation.
- The MGI is defined as the geometric mean of the fold increase in serum HI titres post-vaccination compared to Day 1.
- All CIs are 95% CIs. The 95% CIs for GMT are obtained within each group separately. The 95% CI for the mean of log-transformed titre is first obtained assuming that log-transformed titres are normally distributed with unknown variance. The 95% CI for the GMT is then obtained by exponential-transformation of the 95% CI for the mean of log-transformed titre.
- Handling of missing data: for a given subject and a given immunogenicity measurement, missing or non-evaluable measurements will not be replaced. Therefore, analysis will exclude subjects with missing or non-evaluable measurements.
- Reactogenicity and safety
 - For the analysis of solicited symptom, missing or non-evaluable measurements will not be replaced. Therefore the analysis of the solicited symptoms based on the ES will include only subjects/doses with documented safety data (i.e. symptom screen completed).
 - For the analysis of unsolicited AEs/MAEs/ILIs/SAEs/concomitant medication, all vaccinated subjects will be considered and subjects who did not report an event will be considered as subjects without an event.

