9.2.1. Subject withdrawal from the study

From an analysis perspective, a ‘withdrawal’ from the study refers to any subject who did not come back for the concluding visit foreseen in the protocol.

All data collected until the date of withdrawal/last contact of the subject will be used for the analysis.

A subject is considered a ‘withdrawal’ from the study when no study procedure has occurred, no follow-up has been performed and no further information has been collected for this subject from the date of withdrawal/last contact.

Investigators will make an attempt to contact those subjects who do not return for scheduled visits or follow-up.

Information relative to the withdrawal will be documented in the eCRF. The investigator will document whether the decision to withdraw a subject from the study was made by the subject himself/herself, or by the investigator, as well as which of the following possible reasons was responsible for withdrawal:

- Serious adverse event.
- Unsolicited non-serious adverse event.
- Solicited adverse event
- Protocol violation (specify).
- Consent withdrawal, not due to an adverse event*.
- Moved from the study area.
- Lost to follow-up.
- Other (specify).

*In case a subject is withdrawn from the study because he/she has withdrawn consent, the investigator will document the reason for withdrawal of consent, if specified by the subject, in the eCRF.

Subjects who are withdrawn from the study because of SAEs/AEs must be clearly distinguished from subjects who are withdrawn for other reasons. Investigators will follow subjects who are withdrawn from the study as result of a SAE/AE until resolution of the event (see Section 8.5.1.2).

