10. STATISTICAL METHODS

10.1. Primary endpoints

Reactogenicity and safety

- Occurrence of solicited local and general AEs after each vaccination:
 - Occurrence of solicited local AEs during a 7-day follow-up period (i.e. on the day of vaccination and 6 subsequent days) after each vaccine dose, in all vaccine groups.
 - Occurrence of solicited general AEs during a 7-day follow-up period (i.e. on the day of vaccination and 6 subsequent days) after each vaccine dose, in all vaccine groups.
- Occurrence of unsolicited AEs after each vaccination:
 - Occurrence of unsolicited AEs during a 28-day follow-up period (i.e. on the day of vaccination and 27 subsequent days) after each vaccine dose, in all vaccine groups.
- Occurrence of hematological and biochemical laboratory abnormalities after each vaccination:
 - Any hematological (red blood cells, white blood cells and differential count, platelets count and hemoglobin level) or biochemical (alanine aminotransferase, aspartate aminotransferase, creatinine, blood urea nitrogen [BUN] and BUN-to-creatinine ratio) laboratory abnormality at each visit subsequent to Day 1, in all vaccine groups.
- Occurrence of MAEs, pIMDs and SAEs:
 - Occurrence of MAEs, pIMDs and SAEs throughout the entire study period, in all vaccine groups.

Immunogenicity

Anti-H1 stalk immune response measured by ELISA and by MN assay 28 days after each priming dose:

- Levels of anti-H1 stalk antibody titers by ELISA and by MN assay.

The following aggregate variables will be calculated for the above parameters with 95% confidence interval (CI):

- Seropositivity rates and geometric mean titers (GMTs) at Days 1, 29 and 85.

- Percentage of subjects with a \geq 4-fold increase from Day 1 to Days 29 and 85.
- Percentage of subjects with a \geq 10-fold increase from Day 1 to Days 29 and 85.
- Mean geometric increase (MGI) from Day 1 to Days 29 and 85.

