10.8. Analysis of safety

The analysis will be performed on the ES.

All analyses will be descriptive. Data will be presented by dose, overall/dose and overall/subject. Outputs will be presented by study group. Analyses will be repeated pooling groups according to the adjuvant (AS01, AS03, no adjuvant).

- The percentage of subjects with at least one local AE (solicited and unsolicited), with at least one general AE (solicited and unsolicited) and with any AE during the solicited follow-up period will be tabulated with exact 95% CI. The same calculations will be performed for AEs rated as grade 3.
- The percentage of subjects reporting each individual solicited local and general AE during the solicited follow-up period will be tabulated with exact 95% CI. The same tabulation will be performed for grade 3 AEs and for AEs with relationship to vaccination.
- The verbatim reports of unsolicited AEs will be reviewed by a physician and the signs and AEs will be coded according to the Medical Dictionary for Regulatory Activities (MedDRA). The percentage of subjects with at least one report of unsolicited AE classified by the MedDRA and reported up to 28 days after vaccination will be tabulated with exact 95% CI. The same tabulation will be performed for grade 3 unsolicited AEs and for unsolicited AEs with a relationship to vaccination.
- The percentage of subjects with MAE(s) will be summarized by group with exact 95% CI.
- The percentage of subjects with episode(s) of ILI will be summarized by group with exact 95% CI. **(Amended: 11 July 2019)**
- At each hematology/biochemistry sampling timepoint, by study group, individual hematological and biochemical values will be presented as number of subjects out of range (above and below normal range) and tabulated by toxicity grading (refer to [APPENDIX C](#)). In addition, changes from baseline (median/interquartile range) will be presented.
- SAEs and pIMDs will be described in detail. Withdrawals due to (S)AEs will also be summarized.

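### The MAE and ILI percentages to Month 26 count subjects who leave early as event-free for their unobserved time, so any dropout understates them

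*Protocol*

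**What the plan says.** Section 10.6 sets two different rules for missing safety data. For solicited symptoms nothing is imputed: "Therefore the analysis of the solicited symptoms based on the ES will include only subjects/doses with documented safety data". For unsolicited AEs, MAEs, ILIs, SAEs and concomitant medication the rule is the reverse: "all vaccinated subjects will be considered and subjects who did not report an event will be considered as subjects without an event".

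Section 10.5.1 defines who counts as vaccinated: "The Exposed Set (ES) will include all subjects with at least one vaccine administration documented". It adds: "A safety analysis based on the ES will include all vaccinated subjects".

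Section 10.1 lists among the primary endpoints: "Occurrence of MAEs, pIMDs and SAEs throughout the entire study period, in all vaccine groups". Section 8.3.1 runs MAE and ILI collection from Day 1 to Month 26. Section 10.8 gives the summary measure: "The percentage of subjects with MAE(s) will be summarized by group with exact 95% CI". It plans the same measure for ILI episodes, while SAEs and pIMDs are to be described in detail. On layout it says: "Data will be presented by dose, overall/dose and overall/subject". It also repeats the tables with groups pooled by adjuvant.

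For subjects who leave, Section 9.2.1 says: "All data collected until the date of withdrawal/last contact of the subject will be used for the analysis". Section 9.2 does not replace them. No section states person-time, censoring or a minimum follow-up for these percentages.

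**The concern.** The denominator is fixed at first vaccination, but the numerator can only grow while a subject is observed. Someone last seen around Day 57 has about two months of MAE and ILI data, yet enters the 26-month percentage on the same footing as someone who completed Visit 12 without an event. Unobserved time is scored as event-free time.

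The error has one direction. With any dropout, the crude percentage is below the risk over the full period. If dropout differs between groups, the group with more of it looks better with no difference in true risk. The stated main purpose of the study is the safety of each SUIV compared with IIV4 (Section 1.2.2), so readers will set these percentages side by side even though they are descriptive.

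A smaller point concerns wording. The solicited rule refers to subjects and doses, whereas the rule for unsolicited events refers only to vaccinated subjects. It does not say that a by-dose table is restricted to those who received that dose.

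**Working it through.** **The plan's own figures.** Table 26 (exact 95% intervals, 45 subjects) reproduces with Clopper-Pearson limits to within 0.001 in every row; for example, 5/45 gives 0.037 to 0.241. The precision tables are not at fault. They take the whole group as denominator and do not deal with incomplete follow-up.

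**Inputs from the protocol.** There are 47 subjects per group (Section 4.1). Events are collected from Day 1 to Month 26 (Section 8.3.1). The denominator is all vaccinated subjects, and no report means no event (Section 10.6).

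**Inputs that must be assumed.** The protocol gives no dropout rate at Month 14 or Month 26 and no expected MAE or ILI risk. The nearest figure, 4/47 (9%) non-evaluable, concerns post-primary immunogenicity (Section 10.4.1). I take dropout d of 5% to 20% and true 26-month risk p of 10%, 30% and 50%, with 30% as the central case. The hazard is constant, exits are spread evenly over follow-up, and leaving is unrelated to future risk.

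**Formula.** Let L = -ln(1 - p). A subject who exits at a uniformly distributed time has an event before exit with probability q = 1 - (1 - e^(-L))/L = 1 - p/L. The reported rate is (1 - d)p + dq, so the understatement is d(p - q).

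**Central case, p = 30%.** L = 0.3567 and q = 1 - 0.30/0.3567 = 0.159.
- d = 5%: 0.95 x 0.30 + 0.05 x 0.159 = 29.3%, understated by 0.7 points.
- d = 10%: 0.90 x 0.30 + 0.10 x 0.159 = 28.6%, understated by 1.4 points.
- d = 20%: 0.80 x 0.30 + 0.20 x 0.159 = 27.2%, understated by 2.8 points.

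**Two groups with equal true risk, dropout 5% and 20%.**

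| True risk | Reported, d = 5% | Reported, d = 20% | Spurious difference |
|---|---|---|---|
| 10% | 9.8% | 9.0% | 0.7 points |
| 30% | 29.3% | 27.2% | 2.1 points |
| 50% | 48.9% | 45.6% | 3.3 points |

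(Differences are taken before rounding.)

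**Upper bound for timing.** If every exit came directly after Dose 1, the understatement would be d x p. At p = 30% that is 1.5 points for d = 5% and 6.0 points for d = 20%, a difference of 4.5 points.

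**Against precision.** Table 26 gives 0.112 to 0.371 for 10/45, a width of 25.9 points. The bias in the central case lies well inside that. The adjuvant pools have 3 x 47 = 141 subjects, so their intervals are narrower, while the bias stays the same at the same dropout.

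**By-dose wording.** Suppose 40 of 47 receive the booster and 8 of them report an event. The rate is 8/40 = 20.0% (exact interval 9.1% to 35.6%) among recipients, and 8/47 = 17.0% (7.6% to 30.8%) over the whole group. The counts are invented; they show only what the choice of denominator does.

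**The case against.** The strongest reply is that this is a descriptive Phase I/II study, that a crude percentage of exposed subjects is a transparent summary, and that any bias is lost in the width of the intervals. Withdrawal status is summarised by group (Section 10.7) and withdrawals due to (S)AEs are summarised (Section 10.8), so a reader could see an imbalance. All of that is true and keeps the point modest. But showing dropout does not correct a rate, and the understatement has a known direction. Nor is this a detail left to the statistical analysis plan: the protocol itself states the rule, and Section 10.11 requires departures from it to be justified.

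Several stronger readings are tempting, and the documents do not support them.
- *The whole safety analysis is affected.* Solicited AEs follow the opposite rule, and laboratory values are tabulated by sampling timepoint.
- *SAE and pIMD rates are biased.* pIMDs are not named in the rule, and Section 10.8 plans a description of SAEs and pIMDs, not a percentage.
- *Dose 2 and Dose 3 tables include non-recipients.* Section 10.6 can be read that way, but by-dose presentation, a 28-day window after each dose, and analysis by treatment actually given (Section 10.5.1) all point to recipients. This is an ambiguity, not a stated error.
- *Subjects who leave after a reaction give their group a clean record.* Events up to last contact are counted, so a subject who leaves because of an MAE already has one. Stopping vaccination is also not the same as leaving the study (Sections 6.5 and 9.2.2).
- *The comparisons in Section 10.10 are distorted.* That section concerns reactogenicity and immunogenicity, and its only decision rule is a GMT ratio.

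**Conclusion.** The point holds for the crude MAE and ILI percentages to Month 26. MAEs are a primary endpoint; ILIs are not listed as a separate one. These percentages are understated whenever there is dropout. At a true risk of 30% and 5% to 20% dropout spread evenly, the understatement is about 0.7 to 2.8 points, and 5% against 20% dropout gives a spurious difference of about 2 points. These sizes rest on assumed dropout, assumed risk, a constant hazard and non-informative exit.

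A reader might infer that the group comparisons in this trial are distorted by unequal dropout. The protocol gives neither a Month 26 dropout rate nor any sign of imbalance, so a shift between groups is possible but not shown. The improvement is worth making because it is cheap, not because the likely bias is large.

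**What to change.** In Section 10.8, keep the crude percentages and report next to them, by group and by adjuvant pool, one of these two measures for MAEs and ILIs, and for SAEs if they are tabulated as a rate:
- incidence per person-year from first dose to last contact with an exact Poisson 95% interval (if first events are counted, time at risk ends at the event); or
- Kaplan-Meier cumulative incidence at Month 26.

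Either measure removes the follow-up bias only if leaving is unrelated to future risk, and the report should say so.

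In the same edit, word Section 10.6 so that the vaccinated subjects in a by-dose table are the recipients of that dose, as the layout in Section 10.8 already suggests.

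The cost is one wording change and a few extra tables, using dates of dose, event and last contact that are already collected. Study conduct and sample size do not change. Some rates will look slightly less favourable.
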